
2. Study objectives or hypotheses

a. Hypotheses:

Homozygous carriers of the 118A allele of the μ -opioid receptor will show greater positive subjective response to the morphine than those carrying one or two copies of the

118G allele (118GX), paralleled by lower binding potential for [¹¹C] raclopride following morphine injection because of greater dopamine release than carriers of the G allele.

Objectives:

- a. Primary objectives:** To examine the role of the μ -opioid receptor polymorphism OPRM1 A118G on the subjective and objective effects, including dopamine release, of the μ -opioid agonist morphine.
- b. Secondary objectives:** A number of exploratory analyses will be carried out with the collected data to generate hypotheses on the relation of patient characteristics (e.g. family history of alcohol/drug use disorders, pain, mood, etc.), physiological opiate responses (e.g., pupil constriction, cardiovascular parameters such as respiratory rate and % oxygen saturation as measured by Pulse Ox), endocrine responses (cortisol, ACTH), pain threshold (measured by cold pressor test), MRI scans, and positive psychological effects (as measured via visual analog scale) with DA release measured by PET.

3. Subjects

a. Description of study populations

i. Brief description of subject groups

Subjects will be 21-55 year-old, non-nicotine dependent male volunteers who have taken prescription pain pills without negative effects in the past, but are not currently taking them or dependent on them. All participants will be in good health, non-smokers or light smokers (< 20 cigarettes/week), current non drinkers or social drinkers; participants should not meet DSM IV criteria for alcohol abuse or alcohol dependence. Subjects will be recruited into two groups: 1) subjects homozygous for the major 118A allele (118AA genotype) of the OPRM1 polymorphism; 2) subjects carrying one or two copies of the variant 118G allele (118AG or 118GG genotype, hereafter called 118GX) of the OPRM1 polymorphism.

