At baseline as well as during and after the injection, the following measures will be obtained, following the schedule outlined in the study-session flow-sheet (Table 1): Subjective questionnaires: a visual analog scale of high and intoxication See Appendix I. for Drug Effects Questionnaire (DEQ) (Holdstock and de Wit 1999). The DEQ consists of four visual analog scales used to describe current drug effects (feel drug effects, none (0) to a lot (100)]; like the effects they feel, dislike (0) to neutral (50) to like extremely (100); feel high, not at all (0) to a lot (100); and (4) would like more not at all (0) to a lot (100).

Objective Measurements: 1) Pupil constriction(Grace et al. 2010), cold pressor test (Posner 1991), and 2) Blood will be drawn at baseline and at 10 min after the injection for analysis of blood chemistries potentially responsive to an opiate challenge (including, but not limited to ACTH and cortisol) (Jaffe 1985).

Cold Pressor Test: The cold water pressor test evaluates discomfort or pain when the nondominant hand is first placed in a warm water bath (37° C) for 2 min, then transferred to an ice water bath (0° C). The participant is instructed to immerse his/her hand in the ice water for up to 3 min, but could withdraw the hand at any time if the pain becomes too great. Participants are instructed to report verbally when they first sensed pain. This time measures pain threshold. Time to withdrawal measures pain endurance (Posner 1991). See scoring sheet in Appendix I.

Pupil constriction test: Participants will be instructed to sit quietly, blinking as little as possible while the pupillograph is positioned over the right eye by the operator. While the participant focuses on a fixed point. The resting pupil diameter will be measured for 2 s every 20 s for a total of one minute. This test is a modification of a previously reported method (Grace et al. 2010) to remain within the time of the expected drug effect and will commence four minutes after the participant puts his hand in the cold water.

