At 5 min following the morphine, which will be administered by an NIH Credentialled physician with ACLS certification, or placebo injection, up to 12 mCi [¹¹C]raclopride will be administered as a bolus over one minute into the IV line in the opposite arm. Monitoring of HR, RR, BP, EKG and oxygen saturation will begin immediately by an NIH Credentialled physician. Values will be recorded every 5 min for the duration of the PET scan by the nurse or nurse practitioner monitoring the study. The participant will be asked how he feels in addition to the administration of the DEQ in the event he feels nauseous or needs to vomit. He will also be encouraged to tell the study staff at any time if he feels nauseous or needs to vomit. In the event that the participant experiences either of these side effects, he will be removed from the scanner until the effects subside or if they do not, the study will be discontinued. As the participant cannot easily view the DEQ in paper form or on a computer while he is in the scanner, he will be asked to provide a number between 0 and 100 in response to the four DEQ questions. An NIH Credentialled physician with ACLS certification, will continue to monitor these values for 60 min or until the values return to normal ranges. Dynamic PET scans will begin with the [¹¹C]raclopride injection and continue approximately 90 minutes to obtain optimal signal.

The PET data from the placebo day will be used as a measure of baseline raclopride binding potential, using the Simplified Reference Tissue Model outlined by Lammertsma and Hume (1996). PET measurements taken following the morphine injection will be compared to that derived from placebo injection to measure the reduction in specific binding due to competition with dopamine endogenously released by the morphine challenge. The percent change from baseline has been shown to be proportional to the magnitude of dopamine release (Watabe et al. 2000).

Table for Visits 3 and 4

Minutes	BL	0	5	10	15	20	25	30	35	40	45	50	55	60	70	80	90	95
Morphine or placebo administration		x																
[¹¹ C]Raclopride injection, start scanning			x															
HR, BP, RR, O ₂ Sat, EKG recorded*	x		x	x	x	x	x	x	x	x	x	x	x	x	x	x	x	x
DEQ	x			x		x		x		x		x		x				
End scanning																	x	
VAS																	x	

Please note timing for these parameters will be as close as possible to the stated times, but may not be at exactly these times.

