To evaluate for the possibility of adverse events, a safety assessment evaluation will be conducted at the completion of the last of the PET scan / injection study sessions. This assessment will include vital sign determination, EKG, CBC, and blood chemistry. The Lead Investigator or her designate will contact the participant by phone, approximately one week after the completion of the study to evaluate for the possibility of any unexpected adverse events.

Participants will be withdrawn from the study if they do not follow the instructions outlined in the protocol and informed consent form. Participants will also be withdrawn if they cannot tolerate the morphine injection and demonstrate any signs of untoward effects. Participants may also, at any time, choose to discontinue their participation in the study.

9. Outcome measures

- a. The two primary outcome measures are:
 - 1) $[^{11}\text{C}]\text{raclopride}$ binding potential in striatal areas of the brain
 - 2) Subjective perceptions of morphine intoxication and opiate effects.
- b. Secondary measures are:

- 1) levels of neuroendocrine measures (ACTH, cortisol)
- 2) pupillary constriction, respiratory rate, pain response

10. Statistical Analysis

a. Analysis of data/ study outcomes

For the primary analyses, dependent variables (subjective and objective responses in the laboratory, post-morphine injection raclopride binding potential) will be analyzed using analysis of variance, with genotype as the independent factor. The role of drug and alcohol drinking history and family history of drug abuse/alcoholism as well as self-reports of ancestry and genetically derived ancestry scores will be evaluated as covariates in the analysis. The level of significance will be set at 0.05.

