PET Analysis will be based on a Region of Interest (ROI) methodology. MRI scans will be performed on each participant, and co-registered with the participant's PET scans. ROIs will be drawn in the nucleus accumbens, dorsal and ventral caudate and putamen, these being the main areas of post-synaptic dopamine release. An ROI will also be placed on the cerebellum as this region is thought to be devoid of dopamine receptors and is used as the reference region because it provides a measure of nonspecific binding (Lammertsma and Hume 1996). Dopamine release will be estimated by comparing [¹¹C]raclopride binding potential derived using a bolus injection and the simplified reference tissue model (SRTM) under two different conditions (baseline vs. morphine) during separate scans conducted in randomized order.

Baseline binding potential, changes in binding potential following morphine challenge, and subjective effects of the challenge as measured by changes in stimulation and intoxication scores on subjective perception scales between dose conditions (opiate vs. placebo) will be correlated.

a. Power analysis

Sample size:

In a study that evaluated the effect of remifentanil administration on D2 dopamine receptor availability using a different PET radioligand in detoxified alcohol dependent participants (N=11) and controls (N=11) found a significantly reduced dopamine D2/3 receptor availability after administration compared with baseline in the ventral striatum (9.5%) and the dorsal putamen (8.3%) in both groups (Spreckelmeyer et al. 2011). We can expect similar reductions due to DA release after morphine in one or both research groups (118A homozygotes; 118GX). A study that evaluated the effect of the variants of the OPRM1 genotype in social drinkers compared during placebo and alcohol infusions found a significantly greater DA release as measured by Δ binding potential in those participants who carried the G allele (N=12) compared to the 118 homozygotes (N=16) (Ramchandani et al. 2011). However, results of the studies in the humanized mouse strains of these two genotypes yielded opposite effects of genotype on DA release from morphine.

If the results of this study yield similar results, 40 completers per group should provide adequate power to detect effects of OPRM1 genotype. We estimate that to have this number of completers, we must screen and genotype at least 120 prospective participants.

[figure not shown]

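### Two primary outcomes share one 0.05 level with no success rule and no named region, scale or time summary, and the PET variable in Section 10a is not the placebo-to-morphine change used elsewhere to define dopamine release

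*Combined protocol and SAP*

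**What the plan says.** Section 9 opens with "The two primary outcome measures are" and lists raclopride binding potential in striatal areas (plural) and subjective perceptions of intoxication and opiate effects. Section 10a begins "For the primary analyses, dependent variables (subjective and objective responses in the laboratory, post-morphine injection raclopride binding potential", applies analysis of variance by genotype, and closes with "The level of significance will be set at 0.05".

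The components of each outcome are set out elsewhere:

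- **Regions.** Section 10a states "ROIs will be drawn in the nucleus accumbens, dorsal and ventral caudate and putamen". That is four or five target regions, depending on whether dorsal and ventral also apply to the putamen. None is called primary.
- **Subjective scales.** Section 4d states "The DEQ consists of four visual analog scales used to describe current drug effects". The Visit 2 table schedules the DEQ at baseline and at six times from 10 to 60 minutes, and the DEQ is repeated in the PET sessions. Section 4a and Appendix I add a retrospective visual analog scale (VAS) of peak effects.
- **PET variable.** The opening summary, Section 4a, Section 4d and the region-of-interest paragraph of Section 10a all measure dopamine release by comparing the saline and morphine scans. Section 4d adds "The percent change from baseline has been shown to be proportional to the magnitude of dopamine release".
- **Objective responses.** Section 10a puts these in the primary analyses. Section 9b lists "pupillary constriction, respiratory rate, pain response" as secondary.

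The hypothesis in Section 2 is that A homozygotes "will show greater positive subjective response to the morphine than those carrying one or two copies of the" G allele, with a parallel effect on binding. No section gives an alpha split, a test order or a rule for success.

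**The concern.** Two primary tests at an unadjusted 0.05 give two chances of a false positive if either one would be reported as success. The size of the problem depends on a rule that is not written down.

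The outcomes themselves are also open. A choice of region, scale or time point made after the data are seen could become the primary result, and the PET data are examined early, after five participants per group (Section 15b).

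The PET variable raises a separate matter. A post-morphine binding potential reflects both how many receptors were available at baseline and how much dopamine was released. A genotype difference in that value alone would not show a difference in release, which is the question the study asks.

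**Working it through.** **1. The plan's own figure.** The power section uses one two-group F test with f = 0.65 and alpha 0.05. With N = 22, lambda = 0.65² × 22 = 9.295, the critical F(1, 20) is 4.3512 and power is 0.8263. This matches the document. The calculation covers a single test and does not say which outcome or region.

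**2. One test per outcome, no genotype effect on either.**

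- Either suffices, independent outcomes: 1 − 0.95² = 0.0975. The upper bound whatever the dependence is 2 × 0.05 = 0.10.
- Either suffices, correlated outcomes (simulated two-sided tests, 40 per group): 9.5%, 9.1%, 8.4% and 7.1% at correlations 0.3, 0.5, 0.7 and 0.9.
- Both required: 0.05² = 0.25% if independent, rising to 2.9% at correlation 0.9. The bound is 5%, and it also holds when one of the two effects is real.

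**3. Separate tests of regions and DEQ scales (illustration only).** The counts, four or five regions and four scales, come from Sections 10a and 4d. The correlations are assumptions. The table gives the simulated chance of at least one result below 0.05, with 40 per group. The two figures in each cell are for a correlation of 0 and of 0.3 between the PET and DEQ families.

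| Correlation within each family | 4 regions + 4 scales | 5 regions + 4 scales |
|---|---|---|
| 0.95 | 15.2% / 14.9% | 15.7% / 15.1% |
| 0.9 | 18.1% / 17.6% | 18.6% / 18.2% |
| 0.8 | 21.6% / 20.8% | 22.8% / 22.4% |
| 0.7 | 24.5% / 23.6% | 26.1% / 25.3% |
| 0.5 | 29.0% / 27.7% | 31.0% / 30.2% |

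Full independence would give 1 − 0.95⁸ = 33.7% or 1 − 0.95⁹ = 37.0%. That is unlikely for neighbouring regions that share one cerebellar reference.

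**4. The PET variable.** Write post-morphine binding as B × (1 − r), where B is binding on the placebo scan and r is the fractional reduction from release. Suppose both genotypes have the same r, for example the 9.5% ventral striatal reduction cited in the power section. The post-morphine values are then 0.905 × B in each group, and their ratio equals the ratio of the baselines. Any baseline difference passes straight through to the test, although release is identical. The covariates listed in Section 10a do not include the placebo scan, so nothing in the written model removes it.

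**5. Cost of a split level.** For N = 80, lambda = 80 × f² with 1 and 78 degrees of freedom.

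- The effect detectable with 80% power is f = 0.317 at alpha 0.05 and f = 0.350 at alpha 0.025.
- At f = 0.317, power falls from 80.0% to 70.9%.
- At f = 0.65, lambda = 33.8 and power is 99.99% at 0.05 and 99.97% at 0.025.

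**The case against.** The strongest reply is that Section 2 describes a joint pattern, with the binding effect running parallel to the subjective one. If both must be positive, the error rate never exceeds 5% and no adjustment is needed. This stands as a possible reading, so the 10% figure must be stated as conditional. But Section 2 gives a hypothesis and not a decision rule, and Section 10a does not turn it into one.

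It can also be said that these are two distinct questions in a small physiologic study (Section 15a), each entitled to its own 5%. That bears on severity. It does not supply the missing region, scale or time summary.

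Several stronger readings are tempting but not supported:

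- **That the plan carries a 15-31% error rate.** The documents neither say that regions and scales will be tested separately nor give any correlation. The range reflects the assumed values, and counting the VAS or individual times would change it.
- **That the subjective session is missing.** The opening summary and Sections 4a, 4d and 10a together imply Visit 2. It is only not stated outright.
- **That the PET variable is undefined throughout.** The protocol is consistent in comparing two scans, and the phrase in Section 10a is the outlier. What remains open is absolute difference (opening summary, Section 4a) or percent change (Section 4d).
- **That the inconsistent association studies described in Section 1 show the danger of unplanned endpoint choice.** Section 1 attributes the inconsistency partly to limited power with heterogeneous disease phenotypes.
- **That listing objective responses as primary raises the error rate by a known amount.** Section 9b and the secondary objectives point the other way, while the primary objective in Section 2 also mentions objective effects. This is a wording conflict, and no rate can be attached to it.

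**Conclusion.** The point holds, as a change that should be made. With one test per outcome and no genotype effect, the chance of at least one false primary finding is up to about 10% if either outcome suffices (9.75% under independence). It is at most 5% if both are required. The documents do not say which applies. The 15-31% range is illustrative only, resting on separate testing and on assumed within-family correlations of 0.95 down to 0.5.

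The mismatch over the PET variable needs no such assumption. As written, Section 10a tests a quantity that mixes baseline receptor availability with release. The study is small and physiologic, and the correction needs no new data, so this does not rank as a fatal flaw.

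**What to change.** Before the interim PET look in Section 15b:

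1. In Section 10a, replace the post-morphine binding potential with the placebo-to-morphine change in one named region. The nucleus accumbens is one candidate: Section 10a lists it, and Appendix VII reports the mouse genotype effect there. Choose either percent change or absolute difference, and state the choice.
2. Name one subjective primary: one scale and one time summary at Visit 2, for example area under the curve over 10-60 minutes, morphine minus placebo. The scale is the sponsor's choice and should be justified against the hypothesis in Section 2. Note that placebo always comes first at Visit 2. An order effect common to both genotypes cancels in the genotype comparison, but the morphine effect itself is confounded with order.
3. State the success rule. Either one outcome suffices, with Holm at 0.05 overall (smaller p-value against 0.025, then the larger against 0.05), or both are required, each at 0.05.
4. Label all other regions, scales and times, the VAS, the PET-session DEQ and the objective responses secondary or exploratory, so that Section 10a agrees with Section 9b.
5. Reconcile the stimulation score in the correlation sentence of Section 10a with the instruments collected, since it is not an item of the DEQ or the VAS.

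This costs wording and analysis only, with no added participants or procedures. Under Holm, the detectable effect at the strictest step rises from f = 0.317 to f = 0.350, and PET power at the planning value stays above 99.9%. The documents give no effect size for the DEQ, so its power cannot be stated. Requiring both outcomes has its own price: if each had 80% power and they were independent, joint power would be 0.80 × 0.80 = 64%. Under either rule, an effect confined to another region or scale would count as secondary.

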The requirement that there is experience with prescription pain pills is in place because we do not wish to administer an opiate to naïve volunteers. Prior experience with opioid pain medications enhances safety and aids in the exclusion of potential participants who have had negative experiences (e.g., allergic response, excessive nausea and/or vomiting, itching) as these side effects could make obtaining the PET scan difficult. The experience of an individual who has taken even one or two prescription pain pills should provide enough information regarding negative side effects to eliminate people with allergies or negative experiences. In addition, participants will be excluded if they have used pills chronically (> 6 weeks) or recently (within the previous 3 months). The purpose of these criteria is to remove possible residual effects on the receptor.

We have chosen to restrict the study population to ages 21-55 years to reduce age-related variability in the study. Since the ventral striatum shrinks an average of 3.6 to 3.7% per decade (Gunning-Dixon et al. 1998), a wider age range introduces significant and avoidable variance in the study group.

We have chosen to restrict the study to men only based on the lack of an effect in women on DA release during the administration of alcohol as the effect of alcohol on DA release

is presumed to occur through the μ -opioid receptor (Barr et al. 2007; Mitchell et al. 2012; Urban et al. 2010).

- ii. *Target number of completers:* 80 completers
- iii. Withdrawals or dropouts will be replaced

b. Inclusion criteria

1. Male participants between 21-55 years of age.
2. Good health as determined by medical history, physical exam, EKG and lab tests.
3. Current non-smokers or light smokers or e-cigarette users (<20 cig/week) who can easily abstain from smoking or using e-cigarettes for 1-2 days/week.
4. Current non-drinkers or social drinkers who do not meet past or current DSM IV criteria for alcohol abuse or alcohol dependence.
5. An equal number of final participants will be of OPRM1 118 A/A vs. 118A/G or 118G/G genotype. This means that after the first group (n40) is complete then only participants with the required genotype for the other group will be included.
6. Prior opiate use, at least one experience with one of the opiates in the list in Appendix 1 (p. 34).
7. Comprehension/fluency with English Language.

c. Exclusion criteria

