Post-placebo) and post-morphine injection measures will be made in two areas: 1) subjective response as measured by a standardized questionnaire (DEQ), and 2) objective measures response. We will determine their response to a cold pressor pain test, and a measurement of their pupillary constriction as well as several other tests of their response to the morphine, including continuous Pulse Ox monitoring and intermittent monitoring of their respiratory rate, heart rate, EKG and blood pressure. Blood will be collected to measure plasma ACTH and cortisol levels as they may be suppressed by activation of the μ -opioid receptor. Retrospectively, participants will be asked to evaluate their peak experience to the morphine on a Likert-like visual analog scale (VAS), which will include sedation, euphoria, dizziness, fatigue, depression, tremors, anxiousness, upset stomach/nausea, dry mouth, and headache, which are common side effects of opiate administration (Appendix I). We hypothesize that 118AA subjects will have significantly higher subjective response to the morphine challenge than 118GX subjects.

On two more separate visits, at least a week apart (Visits 3 and 4), participants will report to the Clinical Center in Bethesda for an overnight stay before each PET scan. We will repeat the injection procedure in all participants twice in the PET scanner, once injecting morphine and once injecting saline, and assess the binding potential of [¹¹C]raclopride, a positron emitter labeled ligand which binds preferentially to D2 dopamine receptors. The difference between the binding potential following the saline injection and that during the morphine injection will provide a measure of dopamine release. We hypothesize that 118AA subjects will have a lower binding potential with [¹¹C]raclopride from the morphine injection relative to placebo, indicating greater amounts of dopamine release than those subjects carrying one or two copies of the G allele.

b. Recruitment

This study employs an experiment of nature, i.e. genetic variability, as a basis for group assignment. To obtain the respective groups, this protocol will be conducted in the following phases:

1. Recruitment of potential participants through approved advertising media (see draft ad in Appendix II).
2. Thorough screening of selected participants according to 06-DA-N415 (“Screening Protocol for the Evaluation of Potential Research Subjects”).

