An interim analysis of the PET data is planned after the first 5 participants in each group. The purpose of this analysis is to ensure that dopamine release as evidenced by a reduction in binding potential for [¹¹C]raclopride by the morphine challenge is observed, at least in those participants who are homozygous for the A allele. If no participant (regardless of genotype) exhibits dopamine release, the study will be stopped. If an alternative approach to the study is deemed more likely to allow the measurement dopamine release, such as the use of a different opiate drug or different radioligand, a revised protocol may be submitted.

DSMB Reports

The DSMB will make findings and interpret the data, then report to the PI, IRB, and Clinical Director about continuation, modification, suspension, or termination of the protocol based on observed beneficial or adverse effects of the experimental treatment under study. The DSMB will act promptly on any findings indicating the need for an amendment to the protocol or affecting the continuation of the protocol.

Review Schedule

The DSMB will examine the safety data after the first 10 participants have completed the study. Additional reviews will occur each time the number of study completers (or dropouts) has increased by 20. Additional reviews will be conducted if warranted by the occurrence of serious adverse events or otherwise deemed necessary by the DSMB.

c. Criteria for stopping the study or suspending enrollment or procedures

The study will be stopped after we complete data collection from our target number (80) of participants who complete the study. The study will be stopped prior to that point if an interim analysis does not show any effect of the opiate administration on the release of dopamine. If there are any serious adverse events following the administration of the opiate that are found to be protocol related, the protocol will be suspended until the safety of continuing the protocol can be established or stopped if the safety of continuing the protocol cannot be established.

16. Quality Assurance

a. Quality assurance monitor

The Principal Investigator, Lead Investigator and the MAI will be monitoring data collection and the study on an ongoing basis. Quality assurance (QA) will be performed by NIDA QA and NIAAA QA staff as indicated in the NIDA and NIAAA Quality Assurance Monitoring Planas described below.

b. Quality assurance plan

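### Scan order in the PET sessions is randomised, but the plan does not say whether it is balanced within genotype, and the genotype model has no order term (minor, cheap to fix)

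*Combined protocol and SAP*

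**What the plan says.** Each man has two raclopride PET sessions at least a week apart, one with saline and one with morphine (Section 4a). Section 4a defines the measure: "The difference between the binding potential following the saline injection and that during the morphine injection will provide a measure of dopamine release". The only rule found for which session comes first is in Section 10, Analysis of data/study outcomes: the two conditions are compared "during separate scans conducted in randomized order". The available text gives no method, ratio, block size, stratification or time of assignment.

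On the analysis, the same section says that the dependent variables, including "post-morphine injection raclopride binding potential", "will be analyzed using analysis of variance, with genotype as the independent factor". The candidate covariates are drug and alcohol history, family history and ancestry: "self-reports of ancestry and genetically derived ancestry scores will be evaluated as covariates in the analysis". Scan order is not among them.

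Two accrual rules matter here. Under Section 3b, once one genotype group reaches 40, only the other genotype is enrolled. Under Section 3a, "Withdrawals or dropouts will be replaced", with no statement about the scan order that a replacement receives.

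**The concern.** Dopamine release is a within-man difference between two visits. Suppose the second scan reads differently from the first for reasons unrelated to the drug, such as habituation to the scanner. That shift enters the difference with one sign in men scanned saline-first and the opposite sign in men scanned morphine-first. It cancels from the 118AA versus 118GX contrast only if both groups have the same mix of orders.

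Genotype is not assigned, and the two groups can fill at different times. Even a blocked list that ignores genotype therefore need not balance order within genotype. Replacement without an order rule means that balance at assignment may not survive among completers. With no order term in the model, nothing in the stated analysis removes a chance imbalance. The PET binding potential is one of the two primary outcomes.

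**Working it through.** **The plan's own figure.** One-way analysis of variance with two groups, f = 0.65, alpha 0.05 and N = 22 has lambda = 22 x 0.65² = 9.295 and critical F(1, 20) = 4.3512. Power is 0.8263, which matches the Power Analysis table. With the planned N = 80, the smallest effect detectable at 80% power is f = 0.32, or about d = 0.63 for equal groups. The assumed f = 0.65 corresponds to d = 1.3.

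**Chance imbalance.** Assume simple 1:1 randomisation of order, which the documents neither state nor exclude. The number scanned morphine-first in each genotype is then Binomial(40, 0.5). The difference in proportions, dp, has SD = √(0.5/40) = 11.2 points and mean absolute value 8.9 points. Exact probabilities:

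- at least 10 points (4 men): 43%
- at least 15 points (6 men): 22%
- at least 20 points (8 men): 9.3%
- at least 25 points (10 men): 3.3%

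**Effect on the contrast.** Let delta be the second-minus-first-scan shift. Saline minus morphine changes by −delta if saline is first and by +delta if morphine is first, so the genotype contrast moves by 2 x dp x delta. If post-morphine binding potential alone is analysed, only one scan carries the shift and the contrast moves by dp x delta in raw units. The documents give no delta, so the values below are assumptions. At dp = 0.20:

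| delta (points) | saline minus morphine | post-morphine alone |
|---|---|---|
| 0 | 0 | 0 |
| 1 | 0.4 | 0.2 |
| 3 | 1.2 | 0.6 |
| 5 | 2.0 | 1.0 |

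For scale, Section 10 expects total reductions of 8.3% to 9.5%. At the mean imbalance and delta = 3, the movement is 2 x 0.089 x 3 = 0.5 points.

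**Type I error.** Express the shift as pi, in SDs of the change score. Averaged over random draws of order, simulation (20,000 trials per setting) gives type I error of about 5% for every pi tried from 0 to 1.

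Now fix the split at dp = 0.20. The contrast is displaced by 2 x pi x 0.20, its true SE is √(2/40) = 0.2236, and the unadjusted test rejects beyond 1.991 x 0.2236 x √(1 + 0.96 pi²).

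- pi = 0.25: displacement 0.10, cut-off 0.458. The tails beyond 0.358/0.2236 = 1.60 and 0.558/0.2236 = 2.50 sum to about 6.1% (6.5% by simulation).
- pi = 0.5: displacement 0.20, cut-off 0.496. The tails beyond 0.296/0.2236 = 1.32 and 0.696/0.2236 = 3.11 sum to about 9.4% (9.8% by simulation).

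A noncentral t approximation gives 7.1% and 12.5%. It overstates the error, because with the split fixed the order effect displaces the contrast but does not add to its sampling variance.

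**Power at d = 0.63 (simulated).**

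| Order allocation and model | pi = 0.25 | pi = 0.5 |
|---|---|---|
| Simple, no order term | 77% | 70% |
| Blocked within genotype, no order term | 77% | 72% |
| Simple, order term | 79% | 79% |
| Blocked within genotype, order term | 79% | 79% |

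At pi = 0.5, blocking cuts the true SE of the contrast from √(0.05 x 1.25) = 0.25 to √0.05 = 0.22. Without an order term, the residual SD still contains the order effect, so the test becomes conservative (type I error about 3%) and most of the gain is lost.

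**The case against.** A reader might infer that the trial uses simple, unbalanced randomisation. The documents do not say so. Simple, blocked and stratified schemes all fit the wording, and the probabilities above apply only under the first.

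A reader might also infer that order could systematically create or mask a genotype difference. That does not follow. Random order is unbiased across draws, and with no first-versus-second-scan shift nothing happens at all. The plan also has features that plausibly limit such a shift: time in a mock scanner, both injections already experienced at Visit 2, an overnight stay before each scan, and the same head mask for both. Visit 2 is meant to remove men who react badly before PET, so if order is assigned after it, those dropouts cannot disturb the balance. At the assumed effect of d = 1.3, power is at least 99.9% with or without blocking for shifts up to 0.5 SD.

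A third inference is that the early look is especially exposed: "An interim analysis of the PET data is planned after the first 5 participants in each group". The stopping rule in Section 15b asks whether any participant, of either genotype, shows dopamine release. It does not compare genotypes, so a between-genotype imbalance in order is not a ground for concern there.

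These points make the matter minor, but they do not remove it. The available text states neither the balance of order nor a replacement's order, and the model omits order. The sponsor chose 40 per group in order to reach effects smaller than d = 1.3, and near d = 0.63 a large shift does cost power. The objection that blocking alone achieves little is correct and shapes the fix.

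**Conclusion.** The point holds as a minor gap in design and analysis. Its size rests on two assumptions that the documents do not settle: that order is simply randomised, and that there is a drug-unrelated shift between scans. Under both, about one trial in eleven would have an order imbalance of 20 points or more between genotypes. At exactly 20 points, the saline-minus-morphine contrast would be off by 0 to 2 percentage points over the assumed range of delta. For shifts up to 0.25 SD the displacement is at most 0.10 SD and the loss of power about 2 percentage points, which is small. At 0.5 SD the loss is about 9 points for an effect near d = 0.63, and an order term recovers it. The documents do not support a claim of systematic bias or of an inflated overall type I error.

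**What to change.** In Sections 4d and 10:

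- Allocate scan order 1:1 by permuted blocks of randomly mixed size (for example 2 and 4), from a separate list for 118AA and for 118GX, and state when order is assigned.
- Give each replacement the scan order of the man he replaces, so that completers end close to 20:20 within each genotype.
- Include scan order as a factor in the PET model, whichever PET variable is analysed, so that the standard error reflects the blocking.
- Report scan order by genotype.

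The order term does most of the work on power. Blocking makes order nearly orthogonal to genotype, so the adjustment costs almost no precision; with a 20-point imbalance it would inflate the variance of the contrast by 1/(1 − 0.20²) = 1.04.

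The cost is a few sentences, two pre-generated lists and one degree of freedom. Staff may be able to guess some orders, which mixed block sizes limit. No extra participants, scans or visits are needed.
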